### ***1.10.2 Target Population***

Patients will be screened as they are identified by the clinical trial site. Patients will be selected and approved for inclusion by the Principal Investigator based on inclusion/exclusion criteria as specified in 1.11 Inclusion /Exclusion Criteria of the study protocol, without any limitations to gender or ethnicity.

## **1.11 Inclusion /Exclusion Criteria**

### ***1.11.1 Inclusion Criteria***

1. Males and non-pregnant/non-breastfeeding females at least 18 - 74 years of age.
2. Ability to comprehend the study procedures and signed informed consent.
3. Diagnosed with any the following: acute leukemia (ALL or AML), myelodysplasia, aplasia, and/or therapy (chemotherapy or radiation) induced bone marrow aplasia or hypoplasia with thrombocytopenia (see #6 below) for a minimum of 2 days. Patients who have received either autologous or allogeneic bone marrow transplant, peripheral, or cord blood stem cells may be enrolled if they do not have chronic or acute graft-versus-host disease (GVHD).
4. WHO Grade 1 (subset) or 2 bleeding or at risk for same within 4 weeks of screening. Subset of patients with Grade 1 bleeding are those who have either epistaxis, hematuria, oral petechiae, oropharyngeal bleeding, or bleeding at invasive or other wound sites. WHO Grades 0, 3 or 4 are not inclusion criteria for eligibility.
5. If not hospitalized, willing to be observed in a clinic up to the 6-hour post-infusion time point. Patients may be admitted and observed in the hospital overnight at the discretion of the PI.
6. Thrombocytopenia with platelet count  $\geq 5,000/\mu\text{L}$  and  $\leq 70,000/\mu\text{L}$ .
7. Has permanent address and phone/email for contact and notifications, and available for the duration of the trial, which is expected to be a maximum of 8 weeks.
8. Agrees to not take any nonsteroidal inflammatory drugs within 5 days prior to infusion and during the 6 Day study follow-up period.
9. Agrees to not take any aspirin or aspirin containing drugs within 5 days prior to infusion and during the 6 Day study follow-up period.

10. Agrees to not take any COX-2 inhibitor drugs within 5 days prior to infusion and during the 6 Day study follow-up period.
11. Female patients must have a negative pregnancy test prior to enrollment and during study. Women who are postmenopausal for at least 1 year (>12 months since last menses) or are surgically sterilized do not require this test.
12. Females of childbearing potential should either be surgically sterile (hysterectomy or tubal ligation) or should use an effective, medically accepted contraceptive regimen. An effective method of birth control is defined as those which result in a lower failure rate (i.e., less than 1% per year) when used consistently and correctly such as implants, injectables, combined oral contraceptives, some intrauterine devices (IUDs), abstinence, or vasectomized partner.

### **1.11.2 *Exclusion Criteria***

1. Medical diagnosis of acute or chronic DIC (not based on fibrin degradation products alone).
2. PT or aPTT > 1.3 times the upper limit of normal for the laboratory.
3. Past diagnosis of stroke or thromboembolic events including deep vein thrombosis (DVT), pulmonary embolism, venous or arterial thrombosis, blood clots, or transient ischemic attack (TIA), not to include central or peripheral line-related thrombosis.
4. History of major operative procedures that required general anesthesia in the past 2 weeks.
5. A history or diagnosis of immune thrombocytopenia, thrombotic thrombocytopenic purpura, or hemolytic uremic syndrome.
6. Known inherited disorder of coagulation or platelet function (by history).
7. Receiving active treatment with Plavix (clopidogrel bisulfate) or Ticlid (ticlopidine hydrochloride), or other platelet inhibiting therapy.
8. Receiving tranexamic acid or other antifibrinolitics within 48 hours prior to infusion.
9. Receiving active, inpatient treatment full anticoagulation therapy. Note: a heparin flush may be given daily and before and after blood draws to patients with a central line to keep the line patent. Prophylactic anticoagulation is not a contraindication.
10. History of persistent headaches or migraines. Persistent headaches are defined as the headache frequency is 15 or more days a month for longer than 3 months in the absence of organic pathology.
11. History of an MI, stent placement, had valve replacement and/or repair.
12. For patients with an active acute infection, suspected infection, or a single oral temperature of greater than equal to 101°F or a temperature greater than equal to 100.4° F sustained over a one hour period  in the past 24 hours. Fever related either to the patient's underlying diagnosis (cancer or other neoplastic process) or to the treatment of that disease process is

---

 Silberstein SD, et al. Classification of daily and near-daily headaches: field trial of revised IHS criteria. *Neurology*. 1996;47(4):871.

 Freifeld et al. Clinical Practice Guideline for the Use of Antimicrobial Agents in Neutropenic Patients with Cancer: 2010 Update by the Infectious Diseases Society of America. *Clinical Infectious Diseases*. 2011;52(4):e56-e93.

not an exclusion to study participation. Subjects receiving antibiotics either to treat an infection or as expectant treatment of a clinically-suspected infection are excluded from study enrollment until the infection is resolved or ruled out. Subjects receiving prophylactic antibiotics to prevent an infection are not excluded from study.

13. Systolic blood pressure greater than 160 mmHg or lower than 90 mmHg; or diastolic pressure higher than 100 mmHg.
14. Treatment with any investigational agent within one month before treatment infusion for this trial, other than for treatment of their underlying disease.
15. Unwilling or unable to comply with the requirements of this protocol, including the presence of any condition (physical, mental, or social) that is likely to affect the patient's return for follow-up visits on schedule as determined by the investigator.
16. Other unspecified reasons that, in the opinion of the Investigator or Medical Monitor, make the patient unsuitable for enrollment.
17. Patient is institutionalized because of legal or regulatory order.

### ***1.11.3 Inclusion of Women and Minorities***

The NIH Revitalization Act of 1993, PL 103-43, signed into law on June 10, 1993, directed the NIH to establish guidelines for inclusion of women and minorities in clinical research. It is believed that gender or racial differences will not have an effect on study outcomes, and therefore, the inclusion of women and minorities for this proposed clinical trial is not limited.

## **1.12 Recruitment Process**

Patients will be recruited consecutively as they volunteer and as they meet the eligibility criteria and study timelines.

## **1.13 Sample Size Justification**

For this Phase 1 dose escalation study (Cohorts 1 through 3), there is no statistical basis for the selection of the sample size. The sample size, 8 patients per cohort, was selected to provide a reasonable balance in order to assess safety while minimizing the number of patients potentially at risk. Further details will be given in 1.16 Data Analysis.

## **1.14 Informed Consent Process**

Per 21 CFR Part 50 and 45 CFR Part 46, this clinical trial will require Informed Consent of each patient prior to participation. The informed consent form (original and any amended forms) will be reviewed and approved by IRBs. If acceptable, a central IRB will be designated for use by all participating sites, involved in the conduct of this clinical trial. Additionally, HIPAA Authorizations will be obtained as required.

The informed consenting interview process will be conducted during Visit 1 prior to patient screening activities. Potential patients are provided consent material ahead of time for their review. A member of the research team will review the informed consent form, in a factual

manner, with the individual, in a private area of the study site. The potential patient is allowed time to read the informed consent and then given an opportunity to ask questions. They are given ample time and left alone for as long as is needed before signing the informed consent. A research team member is in the area close-by and the Principal Investigator (PI) (or sub-investigator) is available via phone to answer any questions.

After the potential patients have read the consent, a member of the research team asks the individual whether they have any other questions. It is reiterated during the consent process that they can withdraw from the study at any time. The PI's phone is included in the Informed Consent Form in case they have any questions after signing the informed consent.

The research team member will note any lack of mental capability during the review of the consent with the patient and/or during the question and answer section of the process. If there are any concerns noted by the research team member, they will contact the PI (or sub-investigator) and discuss. The final decision regarding this requirement will be made by the PI (or sub-investigator), after the PI (or sub-investigator) has either:

- Heard clear and convincing information from the research team member that the patient does not meet an entry criterion, or
- Directly interviewed the patient to determine whether entry criteria are met.

As described in additional sections of this Study Protocol, as informed consent is an ongoing process, the interview process at the beginning of each study visit will re-address the information presented during the Informed Consent interview with the intention to confirm the volunteer's acceptance of continued participation. Verbal consent to continue study participation will be obtained prior to additional study procedures performed at that particular study visit.

Ample time and opportunity will be provided for a question and answer session to ensure that the patient can make an informed decision as to whether the research project is of interest. The patient will be encouraged to consult with family, friends or other counsel prior to choosing to participate in the study.

The Informed Consent Form will be initialed (as required by the IRB), signed and dated by the patient and witnessed and dated by the person conducting the consent interview. A signed copy of the consent form will be offered to the patient with the original form kept in study records.

## 1.15 Study Procedure

Patient case report form information will be prepared and provided to the investigational site, outlining the inclusion/exclusion criteria, physical exams, sample collections, and other interventions for each visit. Table 4 on the following pages provides the schedule of the evaluations for each patient.

**Table 4. Schedule of Events**

Evaluation	Initial Screen	Rescreen (if applicable  )	Day 1  Base Line -2 hr pre-infusion	1 hr post infusion ± 15min	6 hr post -1 or +2 hr	Day 2 24 hr post ± 3 hr	If hospitalized			Day 6 (+ 4 days)	Day 30 (+2 days) (by phone)
							Day 3	Day 4	Day 5		
Visit #	1	1A	2	3	4	5	6	7	8	9	10
Sign ICF	X										
Verbal reconfirmation of informed consent		X	X	X	X	X	X	X	X	X	X
History and complete physical exam 	X										
WHO assessment	X	X	X	X	X	X				X	
Abbreviated physical exam 		X	X	X	X	X				X	
Pregnancy test (serum or urine)-applicable females only	X	X									
Concomitant medications (Medications, OTC Remedies, Herbal Preparations,	X	X	X	X	X	X	X	X	X	X	

Evaluation	Initial Screen	Rescreen (if applicable  )	Day 1  Base Line -2 hr pre-infusion	1 hr post infusion ± 15min	6 hr post -1 or +2 hr	Day 2 24 hr post ± 3 hr	If hospitalized			Day 6 (+ 4 days)	Day 30 (+2 days) (by phone)
							Day 3	Day 4	Day 5		
Vitamins, Supplements and IV fluids)											
Record transfused blood products 	X	X	X	X	X	X	X	X	X	X	
Infusion			X								
Vital signs (pulse, BP, RR, temp)	X	X	X	Prior to infusion and then every 15 min ±5 min after the start of infusion until 2 hrs; continue every hour ±5 min until 4 hrs, then at 6 hrs, and 24 hrs post infusion.						X	
Pulse-Ox			X	Continuously monitor while monitoring for vital signs; record at same time points as for vital signs above.							
Monitor for AE			X	Prior to infusion and then every 15 min ±5 min after the start of infusion until 2 hrs; continue every hour ±5 min until 4 hrs, then at 6 hrs, and 24 hrs post infusion, ±10 mins for all other time points. Daily until discharged or Day 6.			X	X	X	X	X 
12-Lead EKG	X		X 		X						

Evaluation	Initial Screen	Rescreen (if applicable  )	Day 1  Base Line -2 hr pre-infusion	1 hr post infusion ± 15min	6 hr post -1 or +2 hr	Day 2 24 hr post ± 3 hr	If hospitalized			Day 6 (+ 4 days)	Day 30 (+2 days) (by phone)
							Day 3	Day 4	Day 5		
Hematology CBC (if blood products are transfused, then CBC pre and post transfusion)	X	X	X	X	X	X	Minimum is daily CBC			X	
ABO group, Rh type	X										
Coagulation Tests: PT/INR, aPTT, D-dimer, Fibrinogen, TAT, PF 1+2, TEG or ROTEM, TGA	Only PT/INR, aPTT, D-dimer, Fibrinogen	Only PT/INR, aPTT, D-dimer, Fibrinogen	X	X	X	X					
Routine Chemistry: Na, K, Cl, CO2, Glucose, BUN, Creatinine, Albumin, Total Bili, Ca, AST, Alkaline Phosphatase, ALT, GGT, LDH, Total Cholesterol, Total Protein			X		X	X					
Special Chemistry hsTroponin I or T Assay			X		X	X					
Draw archive sample	X									X	

Evaluation	Initial Screen	Rescreen (if applicable  )	Day 1  Base Line -2 hr pre-infusion	1 hr post infusion ± 15min	6 hr post -1 or +2 hr	Day 2 24 hr post ± 3 hr	If hospitalized			Day 6 (+ 4 days)	Day 30 (+2 days) (by phone)								
							Day 3	Day 4	Day 5										
 Rescreening performed on those patients who passed eligibility criteria, were not actively bleeding at time of initial screen, and started bleeding within 4 weeks. Patients who were initially screened within 4 days (+6 hrs) do not need to be re-screened except for WHO bleeding assessment and CBC.																			
 Baseline may occur on the same day (within 24 hours) as either Initial Screen or Rescreen. The WHO assessment, CBC and coagulation must be collected at baseline, not more than 2 hours prior to infusion. Red cell transfusion must be specifically related to treatment of bleeding within 24 hours of onset of bleeding.																			
 Chart review for SAEs (only) needs to include data from day 1 though Day 30 (+2 days). Phone call with patient is to confirm if the patient had an SAE or required emergency medical care at an outside facility.																			
 Complete physical exam to include height, weight, general assessment of health by history and medical exam including neurological exam. History to include previous transfusion with red blood cells, plasma and/or platelets.																			
 Abbreviated Physical Exam to include general appearance, cardiovascular, respiratory, extremities, abdomen and head and neck.																			
 In the event of the transfusion of a blood component after infusion of Thrombosomes on Days 1-6, CBC results are required from a sample collected within 8 hours or less prior to the transfusion and within 1-hour (+30 min) post transfusion.																			
 Daily CBC required, but ALL CBC data for each patient during the hospitalization phase through Day 6 must be collected and entered into the database.																			
 If TEG or ROTEM testing is available, include samples for the record.																			
 Repeat EKG if performed more than 4 days before infusion.																			
 For each of the time points that require archive samples, two 10 ml samples will be drawn; one for plasma (EDTA) and one for serum.																			

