**Table 2. Patient Cohort Assignment, Dose and Safety Margins**

Cohort	No. of Infusions	Target Mean Particles per kg	Target Mean TGPU per kg	Estimated Total Vol. Infused based on a 70kg patient and a mean Thrombosomes conc. of $1.61 \times 10^9$ particles per ml with an associated 2800 TGPU per ml 	Safety Margin 	
					Particles infused per kg	TGPU infused per kg
1 (Patients 1-8)	1	$9.45 \times 10^7$	165	4.1 ml	300	301
2 (Patients 9-16)	1	$1.89 \times 10^8$	330	8.2 ml	150	150
3 (Patients 17-24)	1	$3.78 \times 10^8$	660	16.4ml	75	75

Doses will be adjusted per weight of each patient, Estimated Total Volume Infused based on a 70kg patient and a mean Thrombosomes concentration of  $1.7 \times 10^9$  particles per ml with an associated 3400 TGPU. Example Total Dose in ml = (Weight in kg X (desired Dose in particle count or TGPU, specific for each cohort))/ Thrombosomes particle count or TGPU per ml provided with each lot of Thrombosomes. EXAMPLE for Cohort 1:  $70 \times (9.45 \times 10^7) / 1.7 \times 10^9$  per ml = 5.5ml

Safety margin based on the single acute toxicity study in NZWR (MPI 1542-001)

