**Table 6. Requirements Following Patient Withdrawal**

Visit Number	Procedures	Follow-up Required
1 or 1A	Initial screening or Rescreening	None
2 through final visit	Infusion	

• If patient was not infused prior to withdrawing, complete the withdrawal form.

• If infusion was initiated before withdrawal, discontinue the infusion, and complete the final exam and blood draws to assess for safety. Request that patient return for follow-up visits as scheduled to ensure safety. Minimally, obtain patient contact information and perform follow-up phone calls if the patient doesn't come for visits. Provide clinic contact information for procedure-related concerns or patient-initiated follow-up.

• If infusion was completed before withdrawal, complete the final exam and blood draws to assess for safety. Request that patient return for follow-up visits as scheduled to ensure safety. Minimally, obtain patient contact information and perform follow-up phone calls if the patient doesn't come for visits. Provide clinic contact information for procedure-related concerns or patient-initiated follow-up.

Patient interview will be documented by a written record of the interview and patient responses, signed and witnessed by the participant and staff conducting the exit interview at the time of withdrawal.

The anticipated circumstances under which the patient's participation may be terminated by the Investigator are indicated as follows:

- Non-compliance (e.g., no-show for scheduled visit, impairment due to drugs/alcohol, agitation or disruption during visit, inability to follow clinic-established rules concerning conduct)
- Safety issues (e.g., patient does not meet inclusion criteria for ongoing stages of the study, clinic safety due to unacceptable conduct, study cancelled due to product safety)
- Sponsor-initiated study termination
- Investigator-initiated study termination
- IRB of record or FDA study termination

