### **5.2 Safety Population**

The Safety Population will include all patients who were infused with Thrombosomes, regardless of duration of subsequent study participation or adherence to planned follow-up assessments. As patients will be considered enrolled at the start of infusion, the Safety Population will also represent an "enrolled population". The population will be used in descriptive analysis of patient characteristics and disposition, as well as in all safety analyses supporting the Primary Objective and select efficacy analyses supporting the Secondary Objective.

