## 8.6 Infused Thrombosomes

A tabular summary of statistics describing the Thrombosomes infusion doses received by patients will be provided. Specifically, the statistics will describe the following elements:

- Total Volume of Thrombosomes Infused (mL), computed as: ([patient body weight in kg] x [target dose in particles/kg, specific for dose cohort]) ÷ (Thrombosomes lot concentration in particles/mL)
- Interrupted Infusion (Yes/No)
- Reason for Interruption (Adverse Event, Infusion Site or Equipment not Functioning, Patient Declined Infusion, or Other)
- Total Number of Thrombosomes Particles Infused, computed as: (Thrombosomes lot concentration in particles/mL) x (Total Volume of Thrombosomes Infused in mL)
- Total Number of Particles Infused per Kilogram of Patient Body Weight (particles/kg), computed as: (Total Number of Thrombosomes Particles Infused) ÷ (patient body weight in kg)

A data listing will be provided to disclose the elements above for each patient. Note that standard units of calculation and presentation (i.e., particles vs. TGPU and particles/kg vs. TGPU/kg) will be selected prior to database lock. See also Section 3.1, **Table 1**, for more information.

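### SAP 8.6 derives the infused dose per kg from the target dose itself, so the exposure table and listing return the cohort target for every patient, whatever was delivered

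*Protocol*

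**What the plan says.** Dose is set per kg of body weight. SAP Table 1 gives targets of 9.45 × 10^7, 1.89 × 10^8 and 3.78 × 10^8 particles/kg for Cohorts 1 to 3 (165, 330 and 660 TGPU/kg).

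SAP 8.6 describes exposure through three linked quantities:

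- Volume: "Total Volume of Thrombosomes Infused (mL), computed as: ([patient body weight in kg] x [target dose in particles/kg, specific for dose cohort", with the product divided by the lot concentration.
- Particles: "Total Number of Thrombosomes Particles Infused, computed as: (Thrombosomes lot concentration in particles/mL) x (Total Volume of Thrombosomes Infused in mL".
- Particles per kg: "Total Number of Particles Infused per Kilogram of Patient Body Weight (particles/kg), computed as: (Total Number of Thrombosomes Particles Infused", divided by body weight.

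It also reports a yes/no flag for interruption and the reason. The choice between particles and TGPU is left open until database lock. At patient level, "A data listing will be provided to disclose the elements above for each patient". The outputs are Table 14.3.8.1 and Listing 16.2.7.1.

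The documents foresee incomplete infusions. The interruption reasons in SAP 8.6 include adverse events and equipment failure. Protocol Table 6 says: "If infusion was initiated before withdrawal, discontinue the infusion, and complete the final exam and blood draws to assess for safety". SAP 5.2 keeps such a patient in the Safety Population, because everyone infused is included; its stated reasoning begins "As patients will be considered enrolled at the start of infusion".

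On weight, protocol Table 4 footnote 4 reads "Complete physical exam to include height, weight, general assessment of health by history and medical exam including neurological exam". That examination is ticked at Initial Screen only, and SAP Table 2 shows the same ticks.

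**The concern.** The quantity labelled as infused is a planned quantity. It is built from the target, and the later steps undo the division that produced it. No recorded volume enters at any stage, so the summary of particles infused per kg carries no information about delivery.

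Dose per kg is the variable this trial escalates. A reader of the study report will take the exposure table as evidence of what each cohort received. A patient whose infusion was cut short by an adverse event is one whose true dose a Phase 1 reader most wants to know, and that patient would be shown at the full target.

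**Working it through.** **Inputs.** Targets T, a 70 kg patient and a mean lot concentration C of 1.61 × 10^9 particles/mL, all from SAP Table 1. Formulas from SAP 8.6. The fractions delivered are assumptions, because the documents give none.

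**1. Reproduce the plan's volumes.** V = W × T / C:

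- Cohort 1: 70 × 9.45 × 10^7 / 1.61 × 10^9 = 4.11 mL (stated 4.1)
- Cohort 2: 70 × 1.89 × 10^8 / 1.61 × 10^9 = 8.22 mL (stated 8.2)
- Cohort 3: 70 × 3.78 × 10^8 / 1.61 × 10^9 = 16.43 mL (stated 16.4)

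The volume formula in SAP 8.6 is therefore the planning formula of SAP Table 1.

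**2. Follow the chain in SAP 8.6.**

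- Volume: V = W × T / C
- Particles: N = C × V = W × T
- Particles per kg: N / W = T

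W and C cancel. In Cohort 3, patients of 50, 63, 70 and 100 kg have computed volumes of 11.74, 14.79, 16.43 and 23.48 mL, and each gives 3.78 × 10^8 particles/kg. Over 100,000 random combinations of weight, concentration and cohort, the largest relative departure from T was 3 × 10^-16, which is rounding error. Within a cohort the SD is 0 and minimum = maximum = target. The algebra is the same in TGPU. It requires only that the same weight and concentration are used in all three lines, which is how SAP 8.6 writes them.

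**3. Part-delivered infusion, 70 kg, Cohort 3.** True dose = delivered volume × C / W.

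| Fraction delivered (assumed) | Volume given | True particles/kg | Reported | Reported / true |
|---|---|---|---|---|
| 25% | 4.11 mL | 9.45 × 10^7 (Cohort 1 target) | 3.78 × 10^8 | 4.0 |
| 50% | 8.22 mL | 1.89 × 10^8 (Cohort 2 target) | 3.78 × 10^8 | 2.0 |
| 75% | 12.33 mL | 2.835 × 10^8 | 3.78 × 10^8 | 1.33 |

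**4. Effect on a cohort summary.** Suppose one of eight Cohort 3 patients stops at 50% and the other seven receive the target. The true mean is (7 × 3.78 + 1.89) / 8 = 3.54, in units of 10^8 particles/kg, and the true minimum is 1.89 × 10^8. SAP 8.6 reports 3.78 × 10^8 for both.

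**The case against.** **Dosing problems are not invisible.** A reader might infer that the report cannot show a partial dose or a dosing error at all. That goes too far. The interruption flag and reason stand in the same table and listing. SAP 7.2 has a deviation category for departures in giving the study drug, with a summary and a patient listing. What stands is that neither gives a delivered quantity, so a flagged patient still reads as fully dosed.

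**Nothing inferential depends on the value.** A reader might infer that escalation decisions or test results are affected. The documents do not support that. Results are presented by cohort and overall (SAP 8 and 9), no covariate-adjusted analysis is planned (SAP 6.5), and the DMC tables and listings named in SAP Appendix 1 include no exposure table.

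**The data may exist.** The case report forms and the EDC dose table are not among the documents, so the actual volume may be recorded. That makes the fix cheaper, but SAP 8.6 as written would not use it.

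**Particles against TGPU.** Protocol Table 2 footnote 1 allows dosing by "desired Dose in particle count or TGPU, specific for each cohort". At that footnote's 1.7 × 10^9 particles and 3400 TGPU per mL, the Cohort 3 TGPU target gives 660 / 3400 × 1.7 × 10^9 = 3.30 × 10^8 particles/kg, 12.7% below the particle target. It is tempting to call this a hidden dosing error. It needs TGPU dosing, reporting in particles and that one pairing of concentrations. At 1.61 × 10^9 and 2800 the gap is +0.4%, SAP 8.6 leaves the unit open, and the TGPU target is itself a protocol target.

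**Out-of-date weights.** A reader might infer that patients are routinely dosed on a weight up to 4 weeks old. The schedule ticks permit this only for rescreened patients; those bleeding at screening are due for infusion within 4 days. SAP 3.1, SAP Table 2 footnote 1 and SAP Table 3 footnote 1 all imply a full rescreen, which would renew the weight. The size is assumed: a 10% loss gives 1 / 0.90 = 1.11 times target and a 5% gain gives 1 / 1.05 = 0.95, small against two-fold dose steps. This is a minor clarification and does not carry the point.

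**Conclusion.** The point holds for SAP 8.6. As written, the infused dose per kg equals the cohort target for every patient, in either unit. This is exact algebra and needs no assumption about weight, lot or delivery. The overstatement for a part-infused patient is the reciprocal of the fraction delivered: two-fold at an assumed 50%. How often that would occur is unknown. The documents give no interruption rate, and infusions are short (about 16 minutes for 16.4 mL at the protocol's 1 mL/min).

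The consequence is a misleading descriptive line in Table 14.3.8.1 and Listing 16.2.7.1. It does not affect any planned test or the listed DMC package. It should be corrected because these are the outputs that report the dose received in a dose-escalation trial, and the correction is simple.

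**What to change.** In SAP 8.6:

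1. Relabel the computed volume (weight × target / concentration) as the planned volume.
2. Add the recorded volume actually infused as a separate item.
3. Compute total particles (or TGPU) as recorded volume × lot concentration, and divide by the patient's latest pre-infusion weight, in line with the baseline rule in SAP 6.3.
4. Show planned and actual values side by side in Table 14.3.8.1 and Listing 16.2.7.1.

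The cost is a reworded formula and one case report form field, if infused volume is not already captured. No target dose, eligibility rule or sample size changes.

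Optionally, state which weight sets the dose for rescreened patients and reconcile the schedule ticks with the SAP's full-rescreen wording. Adding a Day 1 weighing would go further: it changes the protocol schedule, and protocol 1.22.4 sends non-administrative changes to the IRB and FDA. The correction to SAP 8.6 does not depend on it.
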